7.5.1. Prior Medication

Any medication with a stop date prior to the first dose date for study 603A will be considered a prior medication.

No summary for prior medication will be presented. Prior and concomitant medications will be presented together in a single listing. The listing will be ordered by subject number, and medication start/end dates. Prior medication for study 603A will be flagged separately.

7.5.2. Concomitant Medication

A concomitant medication is any medication that the subject has been taking prior to the first dose of double blind study medication and that the subject is expected to continue to take for some portion of the study treatment period, as well as any medication other than the investigational product that the subject takes during the course of the study treatment period. Concomitant medication for 603B will be summarized by treatment received during the withdrawal period.

A rescue medication is defined as a dose increase of an existing blood pressure medication or initiation of a new blood pressure medication for the purpose of lowering blood pressure. Medications prescribed for other indications are not considered rescue medication. Replacing a blood pressure lowering medication with another medication of the same class within the recommended dose will not be considered a rescue medication. Rescue medication will be summarized for 603A, 603B run-in period, 603B, and integrated. For period-specific summaries of 603A and 603B, rescue medication will be summarized for the period during which the medication started or the dose increased. For integrated summaries, any rescue medication started or dose increased during bexagliflozin treatment will be included.

Concomitant medications will be presented in summary tables for

- 1) 603A, based on the 603A safety analysis set;
- 2) 603B, based on the safety analysis set for withdrawal period;
- 3) Integrated, based on the integrated safety analysis set.

Medication is considered to be concomitant to 603A, the 603B run-in period, or 603B, if it satisfies the conditions below:

- The start date is before the last dose of the study medication for that period;
- The end date is after the first dose of the study medication for that period or the medication is ongoing.

For integrated summaries, medication is considered to be concomitant to bexagliflozin if it satisfies the condition below:

- The start date is before the last dose of bexagliflozin;
- The end date is after the first dose of bexagliflozin or the medication is ongoing.

In the case of completely missing stop date, medication will be assumed to be concomitant to all treatment periods.

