### Study 603A, cumulative weeks 7-12

- Follow procedures for visits 5 and 6 to obtain 24-h ABPM and collect safety data
- Start visit 6 (start of 603B) without rescue medication. If a hypertensive emergency appears imminent, refer the subject to seek urgent care in a clinic or hospital. Prescribe rescue medication at Visit 7 if SBP shows an increase of 30 mm Hg from baseline or exceeds 189 mm Hg in office measurements and continue study activities

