**Table 1. Guidance for Hypertension Rescue Medication Use**

Study/ Cumulative weeks	Procedure
603A weeks 1 to 6	

Follow procedures for visits 10 and 11 as early termination visits to obtain 24-h ABPM and collect safety data

Rescue medication should not be administered unless hypertensive emergency appears imminent. In those situations, refer the subject to seek urgent care in a clinic or hospital. Subject should withdraw from participation in the study and see primary care provider to start or intensify anti-hypertensive therapies

603A weeks 7 to 12	

Follow procedures for visits 5 and 6 to obtain 24-h ABPM and collect safety data

Start visit 6 (start of 603B) without rescue medication. If a hypertensive emergency appears imminent, refer the subject to seek urgent care in a clinic or hospital. Prescribe rescue medication at Visit 7 if SBP shows an increase of 30 mm Hg from baseline or exceeds 189 mm Hg in office measurements and continue study activities

603B weeks 13 to 18	

Obtain 24-h ABPM and collect safety data

Rescue medication should not be administered unless hypertensive emergency appears imminent. In those situations, refer the subject to seek urgent care in a clinic or hospital. Prescribe rescue medication at Visit 7 if SBP shows an increase of 30 mm Hg from baseline or exceeds 189 mm Hg in office measurements and continue study activities

603B weeks 19 to 24	

Obtain 24-h ABPM and collect safety data

Prescribe rescue medication if SBP shows an increase of 30 mm Hg from baseline or exceeds 189 mm Hg in office measurements and continue study activities

603B weeks 25 to 36	

Obtain 24-h ABPM and collect safety data

Prescribe rescue medication if SBP shows an increase of 30 mm Hg from baseline or exceeds 189 mm Hg in office measurements and continue study activities

Choice of rescue therapy should take into consideration current antihypertensive treatment, as well as co-morbidities, such as cardiovascular or renal disease, and severity of BP elevation. Site investigators should use their best clinical judgement when determining rescue medications.

The following strategies are recommended, but not required:

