8.1.1.2. Sensitivity Analysis

Sensitivity analyses will be conducted to examine the robustness of the inference:

- If subject receives rescue medication and has an ABPM value after rescue medication, this value will be analyzed as an outcome. In study 603A, a subject who requires rescue medication will attempt to complete an ABPM before initiating rescue medication. A subject will be terminated if rescue medication starts within the first 6 weeks, or will start study 603B (after the first 6 weeks). No post-rescue medication value is expected and as a result, analysis of post-rescue data will not be conducted. This sensitivity analysis will only be conducted if >5 subjects have post rescue medication values.
- Subjects without scheduled Week 12 assessment (i.e., post baseline ABPM for subjects who did not complete 12 weeks treatment) will be excluded from the analysis.
- A tipping point analysis will be conducted for subjects without Week 12 assessments. The following steps will be taken:
 - If subject has withdrawn from the study or has initiated rescue medication, the value will be considered as missing.
 - A regression model will be used to impute the missing change value using SAS PROC MI procedure. Covariate will include baseline 24-hr mean SBP, diabetes status (history of T2DM or not), renal function (eGFR at screening), pre-treatment status (presently medicated for hypertension or not) and randomized treatment. One hundred datasets will be imputed.
 - If subjects with missing values are in the placebo treatment arm, the imputed value will be used in the analysis.
 - If the subject is in the bexagliflozin treatment arm, a series of δ mm Hg will be added to the imputed values. The δ value will range from 0.5 to 5, with step size of 0.5.
 - The same ANCOVA analysis from Section 8.1.1.1 will be conducted for each imputed dataset and δ . The results will be combined using PROC MIANALYZE in SAS.
- Wilcoxon rank sum test will be conducted including all post baseline ABPM SBP values. For a subject who has no post baseline assessment, the worst outcome within the treatment group (i.e., change from baseline = the maximum increase from baseline in the same treatment group) will be considered.

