A summary and ANCOVA model will be presented as in section 8.1.1.1. The model will include baseline HbA1c in place of baseline mean ambulatory SBP. Baseline 24-hour ambulatory SBP will also be included as covariate.

8.1.3.7. The proportion of subjects requiring any rescue medication at week 12

The summary and analyses will be provided as in section 8.1.2.1 primary analysis.

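### Counted by drug start, the 603A exploratory rescue endpoint would miss most subjects who met the rescue criterion on their 603A arm

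*SAP*

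**What the plan says.** SAP 4.1.3 and 8.1.3.7 list a 603A exploratory endpoint: "The proportion of subjects requiring any rescue medication at week 12". The method is one line: "The summary and analyses will be provided as in section 8.1.2.1 primary analysis". SAP 8.1.2.1 fits a logistic model with terms for diabetes status, eGFR, pre-treatment status, baseline ambulatory SBP and treatment. Its responder is defined from the last blood pressure value before rescue.

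SAP 7.5.2 holds the SAP's only rescue definition and counting rule. The definition is "A rescue medication is defined as a dose increase of an existing blood pressure medication or initiation of a new blood pressure medication", given to lower blood pressure. For the period summaries, "rescue medication will be summarized for the period during which the medication started or the dose increased". Across periods, "For integrated summaries, any rescue medication started or dose increased during bexagliflozin treatment will be included".

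Protocol Table 1 (section 5.7, with the same guidance in 3.1.3) says what happens to a subject who meets the rescue criterion during 603A:

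- Weeks 1 to 6: "Rescue medication should not be administered unless hypertensive emergency appears imminent". Early-termination procedures are done and the subject withdraws.
- Weeks 7 to 12: visits 5 and 6 are brought forward, and the instruction is "Start visit 6 (start of 603B) without rescue medication". Rescue follows at Visit 7 only if the office SBP threshold is met there.

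From visit 6 every subject takes bexagliflozin for 12 weeks (SAP 3.8.1).

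**The concern.** The endpoint is meant to compare rescue need between the randomized 603A arms. The management rules are built so that rescue seldom starts while a subject is still in 603A, yet start is what the SAP counts. A subject who reaches the threshold on the 603A treatment is then absent from the 603A count, and some reappear later under bexagliflozin. The reader of the 603A table would see few events in either arm and could take that as little rescue need, or as no difference in rescue need. Neither conclusion would follow.

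**Working it through.** **Plan figures.** Neither document gives a rescue rate, so no stated figure bears directly on the point. Arm size and SD are borrowed from the sample-size section (SAP 3.7), so that section was checked first. For 603B, n per arm = 2 × (1.960 + 1.036)² × 15² / 4² = 252.5, so 253 by the normal formula. The t-based value is 253.5, which rounds up to the stated 254. Then 508 / 0.75 = 677.3, so 678, against 680 planned. Arm size in 603A is 680 / 2 = 340.

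**Step 1: trace each route against the start-date rule.**

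| Event in 603A | What the protocol does | Where a start-date count puts it |
|---|---|---|
| Criterion met, weeks 1–6, no emergency | Withdraws without study rescue | Not in the 603A count |
| Emergency imminent | Urgent care | Possibly 603A |
| Criterion met, weeks 7–12, threshold not met at Visit 7 | No rescue | Nowhere |
| Criterion met, weeks 7–12, threshold met again at Visit 7 | Rescue starts at Visit 7 | 603B run-in and integrated bexagliflozin |
| Investigator raises background therapy to lower BP (Protocol 5.2.2) | Rescue by definition | 603A |

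Only the second and last rows can put an event in 603A.

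**Step 2: does the reference to SAP 8.1.2.1 supply an event?** No. That section classifies subjects by a blood pressure value. It does not say who needed rescue. Its five-term logistic model would also be unstable, or not estimable, with very few events.

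**Step 3: how many could move to the run-in (all rates assumed).** Let p be the share meeting the criterion in an arm, s the share of those in weeks 7–12, and k the share of those who meet the threshold again at Visit 7. Then:

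- triggers = 340p
- withdrawn = 340p(1 − s)
- booked to the run-in = 340p·s·k
- never started = 340p·s(1 − k)

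Placebo arm, p = 5%, s = 0.5: triggers 340 × 0.05 = 17; withdrawn 8.5; entering 603B 8.5. For k = 0, 0.25, 0.5 and 1, the number booked to the run-in is 0, 2.1, 4.25 and 8.5. With s = 0.5, the range over k is 0 to 3.4 at p = 2% and 0 to 17 at p = 10%. With s = 0.75, it is 0 to 12.75 at p = 5%. The bexagliflozin arm follows the same path: at half the placebo rate (p = 2.5%, s = 0.5) it adds 0 to 4.25.

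**Step 4: what a criterion-based endpoint could show (illustration).** Assume that the plan's ambulatory SD of 15 mm Hg stands in for office SBP, and that mean change is 0 on placebo and −5 on bexagliflozin. P(rise ≥ 30) is 1 − Φ(30/15) = 2.3% and 1 − Φ(35/15) = 1.0%. Power for 340 per arm is Φ{[d − 1.96√(2p̄(1−p̄)/n)] / √[(p₀(1−p₀)+p₁(1−p₁))/n]}, where d = p₀ − p₁ and p̄ is their mean.

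| SD | Placebo | Bexagliflozin | Subjects of 340 | Power |
|---|---|---|---|---|
| 12 | 0.6% | 0.2% | 2.1 vs 0.6 | 15% |
| 15 | 2.3% | 1.0% | 7.7 vs 3.3 | 26% |
| 18 | 4.8% | 2.6% | 16.2 vs 8.8 | 33% |

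This leaves out the criterion of SBP above 189 mm Hg, which would raise the rates, and the three-day confirmation, which would lower them. The normal approximation is rough at these counts.

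**The case against.** The strongest reply is that the 7.5.2 sentence governs medication summaries and that 8.1.3.7 does not cite it. The endpoint speaks of *requiring* rescue, and SAP 8.1.1.2 separates requiring from starting: a subject who requires rescue tries to complete an ABPM first. On that reading, subjects who meet the criterion in 603A already count there. This stands as a possible reading. It is also the reason a definition is needed, because the SAP never adopts it and its only written rule is by start.

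Three stronger readings are tempting, and the documents do not support them.

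- *The endpoint cannot show a difference whatever the truth.* Emergencies and investigator-initiated increases can place rescue inside 603A, and the SAP itself allows for early starts: "A subject will be terminated if rescue medication starts within the first 6 weeks, or will start study 603B (after the first 6 weeks". Without a stated rate, a count close to zero is an inference.
- *Rescue caused by the placebo period is charged to bexagliflozin.* Weeks 1 to 6 cases withdraw and never reach the run-in. Visit 7 rescue needs a new qualifying reading, about six weeks or more into bexagliflozin, and subjects from both 603A arms follow this path. The run-in has no comparator, so no randomized contrast is biased.
- *Visit 7 rescue should be reassigned to the 603A arm.* Attribution by start date agrees with SAP 9.3.2, which tabulates adverse events under the treatment taken at onset. Reassignment would credit placebo with rescue begun on bexagliflozin.

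It is also fair to say that a redefined endpoint would remain weak, as Step 4 shows.

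**Conclusion.** The point holds in a limited form. If the endpoint is counted by drug start, and Table 1 is followed, it captures little beyond emergencies and investigator-initiated increases and cannot describe rescue need by 603A arm with any completeness. Some weeks 7 to 12 cases from either arm will be seen only in the run-in and integrated summaries. Integrated summaries are by default pooled over all subjects (SAP 6.1), so their 603A arm is not visible there. The number is unknown. The scenario figures in Step 3 show its dependence on assumed rates and are not estimates.

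The consequence is confined to one exploratory endpoint and descriptive rescue tables. The start-date rule does not define the primary ambulatory SBP analysis. A reader might infer a threat to 603B, because needing rescue before week 24 is also a balancing group and a term in that ANCOVA (SAP 3.8.1, 8.2.1.1). That factor is fixed before the second randomization, and nothing here shows that it biases the comparison.

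**What to change.** In SAP 8.1.3.7, replace the reference to the 8.1.2.1 responder rule with an event definition: the protocol rescue criterion met during 603A, or rescue started in 603A, or withdrawal or early completion of visits 5 and 6 for that reason. Analyse it by 603A randomized arm. If events are too few for the five-term model, report counts and percentages by arm.

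In SAP 7.5.2, keep attribution by start date. Add a flag for Visit 7 rescue that follows a 603A trigger, and show run-in rescue by 603A arm.

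Protocol 5.7 and SAP 7.5.2 define rescue by a dose increase or new drug, while Protocol 6.13 refers to treatment continued beyond two weeks. These passages should be reconciled so that the started-rescue part of the event has one meaning. The clinical rescue guidance is unchanged, and no view is taken on it.

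The cost is SAP wording and one derived flag. The flag assumes that the reason for early visits 5 and 6, or for withdrawal, can be recovered. Protocol 6.14 records withdrawal reasons, but no field is described for the criterion being met or for the reason visits were brought forward. Events may still be few.

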### **2.4 Safety Objectives**

The integrated safety objectives will assess the hazard ratio for adverse events associated with bexagliflozin exposure compared to placebo in all segments of both studies in which a placebo-exposed cohort is present. The assessments will include:

- the frequency and severity of treatment emergent adverse events
- the frequency and severity of treatment emergent adverse events of special interest
- changes in concomitant medication use
- changes in laboratory test values
- changes in cardiac rhythm determined by 12-lead ECG
- changes in vital signs
- effects on general health detected by physical examination

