4.3. INTEGRATED ANALYSES

Assessments for studies 603A and 603B will be combined to further assess the effectiveness of bexagliflozin after treatment of 12, 24, and 36 weeks.

There are four (4) separate treatment sequences after combining studies 603A and 603B (Table 2).

Table 2 Treatment Sequences for combined studies 603A and 603B

Sequence	Period 1	Period 2	Period 3
Seq 1 PBB	(603A) placebo	(603B) bexagliflozin	(603B) bexagliflozin
Seq 2 PBP	(603A) placebo	(603B) bexagliflozin	(603B) placebo
Seq 3 BBB	(603A) bexagliflozin	(603B) bexagliflozin	(603B) bexagliflozin
Seq 4 BBP	(603A) bexagliflozin	(603B) bexagliflozin	(603B) placebo

The following secondary endpoints will be assessed:

- Change in mean ambulatory SBP or DBP after 12 weeks treatment with bexagliflozin using week 12 assessments for Seq 3 or 4 (end of Period 1) and cumulative week 24 assessments for Seq 1 or 2 (end of Period 2);
- Change in mean ambulatory SBP or DBP after 24 weeks treatment with bexagliflozin using cumulative week 24 assessments for Seq 3 or 4 (end of Period 2) and cumulative week 36 assessment of Seq 1 (end of Period 3);
- Change in mean ambulatory SBP or DBP after 36 weeks treatment with bexagliflozin using cumulative week 36 assessments for Seq 3 (end of Period 3);
- Change in seated office SBP or DBP after 12 weeks treatment with bexagliflozin using week 12 assessments for Seq 3 or 4 (end of Period 1) and cumulative week 24 assessments of Seq 1 or 2 (end of Period 2);
- Change in seated office SBP or DBP after 24 weeks treatment with bexagliflozin using cumulative week 24 assessments for Seq 3 or 4 (end of Period 2) and cumulative week 36 assessments for Seq 1 (end of Period 3);
- Change in seated office SBP or DBP after 36 weeks treatment with bexagliflozin using cumulative week 36 assessments for Seq 3 (end of Period 3).
- Cumulative mean change from baseline in seated office SBP as a function of time (including all scheduled office visits) for subjects exposed to bexagliflozin
- Cumulative mean change from baseline in seated office DBP as a function of time (including all scheduled office visits) for subjects exposed to bexagliflozin

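### SAP 7.5.2: the missing-stop-date rule also waives the start-date condition, so drugs started later can enter the 603A and integrated bexagliflozin concomitant-medication tables

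*SAP*

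**What the plan says.** SAP 7.5.2 (Concomitant Medication) defines concomitance to 603A, the 603B run-in period or 603B by two conditions that must both hold:

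- Start: "The start date is before the last dose of the study medication for that period".
- End: "The end date is after the first dose of the study medication for that period or the medication is ongoing".

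The integrated summary uses the same pair relative to bexagliflozin dosing. Its start condition is "The start date is before the last dose of bexagliflozin".

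The section closes with the rule for incomplete records: "In the case of completely missing stop date, medication will be assumed to be concomitant to all treatment periods". No start-date qualifier is attached. SAP 6.3 places missing-data rules in Sections 7 to 9, and nothing there restores a start-date limit for medications. SAP Section 12 does not mention the rule.

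The section lists three concomitant-medication tables: 603A, 603B (withdrawal period) and integrated.

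**The concern.** When a stop date is missing, the end-date condition cannot be evaluated and some assumption is needed. The start-date condition can still be evaluated. A rule that sets every period to concomitant discards that known date and can place a drug in a period that ended before the drug was taken.

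Protocol 2.4 lists "changes in concomitant medication use" among the safety assessments, and SAP 3.4 and 4.4 carry concomitant medication as a safety objective and endpoint. The 603A table is the one in which randomised arms are set side by side over the first 12 weeks. Drugs begun after all subjects have moved to bexagliflozin do not belong in it. Drugs begun after bexagliflozin was withdrawn do not belong in a table of medications concomitant to bexagliflozin.

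**Working it through.** The plan states no figure on this point, so there is none to reproduce. The check applies the SAP 7.5.2 conditions to a drug with a recorded start date, a completely missing stop date and no ongoing flag.

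**Inputs**

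- Nominal periods in cumulative weeks (SAP Table 1): 603A 0–12, 603B run-in 12–24, 603B 24–36.
- Sequences ending on placebo (SAP 4.3, Table 2): "Seq 2 PBP (603A) placebo (603B) bexagliflozin (603B) placebo" and "Seq 4 BBP (603A) bexagliflozin (603B) bexagliflozin (603B) placebo". In both, the last bexagliflozin dose falls at about cumulative week 24. In PBB and BBB it falls at about week 36.
- Start times tried: cumulative weeks −10, 3, 15 and 30.

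**Two readings**

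- *As written*: missing stop date → concomitant to every period. Period 2 is bexagliflozin in all four sequences, so the drug is also concomitant to bexagliflozin in all four.
- *Start date kept*: missing stop date satisfies the end-date condition only. The drug counts for a period if start < last dose of that period, and for the integrated table if start < last bexagliflozin dose.

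**Results**

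| Start (week) | Periods, as written | Periods, start date kept | Integrated, as written | Integrated, start date kept |
|---|---|---|---|---|
| −10 | 603A, run-in, 603B | 603A, run-in, 603B | all four sequences | all four sequences |
| 3 | 603A, run-in, 603B | 603A, run-in, 603B | all four sequences | all four sequences |
| 15 | 603A, run-in, 603B | run-in, 603B | all four sequences | all four sequences |
| 30 | 603A, run-in, 603B | 603B only | all four sequences | PBB and BBB only |

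For week 15, 15 < 12 is false, so 603A should drop out. For week 30, 30 < 12 and 30 < 24 are both false, so 603A, the run-in, and the integrated count in PBP and BBP should drop out.

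**Reading the differences against the listed tables**

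1. *603A table.* Starts at weeks 15 and 30 are both counted wrongly. In a PBB or PBP subject, a drug begun at week 15 was first taken on bexagliflozin, yet it appears in the 603A placebo column.
2. *Integrated bexagliflozin table.* A start at week 30 is counted wrongly in PBP and BBP. In PBB and BBB it is counted correctly, because those subjects are still on bexagliflozin.
3. *603B table.* All four starts are handled the same way under both readings.
4. *Run-in.* The flag differs for week 30, but no run-in concomitant-medication table is listed.

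**The case against.** The strongest reply is that the sentence follows a two-part test and concerns only a missing stop date. It may have been meant to fill in the end-date condition and leave the start-date condition in force. That is a plausible intention, but the words say all treatment periods without qualification, and a programmer following them would set every flag. The reply supports the fix more than it removes the problem.

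Other limits stand, and several stronger conclusions that a reader might draw are not supported:

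- *That every drug without a stop date is caught.* Drugs flagged ongoing have their own branch in the end-date condition, and that branch keeps the start-date test. Only records neither dated as stopped nor flagged ongoing need the rule. The sentence does not expressly exclude ongoing records, so code keyed on a blank stop date could sweep them in, but that would be a programming error rather than what the section prescribes.
- *That a record is multiplied across three period tables.* There is no listed run-in table, and SAP 7.5 counts each subject once per class and drug name. A misplaced record adds nothing where the subject is already counted.
- *That the integrated table moves use from a placebo column to a bexagliflozin column.* Under SAP 6.1 integrated summaries are by total unless otherwise specified, so the error there is an extra count in the total.
- *That about 255 subjects measures the size.* 680 × 0.75 / 2 = 255 is planned 36-week completers per arm. It is neither the number re-randomised at week 24 nor a count of affected records.
- *That rescue medication or efficacy is distorted.* For rescue, "rescue medication will be summarized for the period during which the medication started or the dose increased", whatever the stop date, and no efficacy analysis uses this rule.

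The single medication listing in SAP 7.5.1 is ordered by subject and start/end dates, so a misplaced record could be traced. That helps a careful reader but does not correct the tables.

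**Conclusion.** The point holds as a minor error in a stated rule. Followed as written, SAP 7.5.2 counts in the 603A table drugs that started after the last 603A dose. It also counts in the integrated bexagliflozin table drugs that PBP and BBP subjects first took after their last bexagliflozin dose. Both contradict the section's own start-date conditions.

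The reach is limited to the descriptive 603A and integrated concomitant-medication tables. The documents give no rate of completely missing stop dates, so the number of affected records cannot be derived, and it may be small. The conclusion assumes that the sentence is programmed literally, that the start date is recorded, and that period boundaries fall at their nominal weeks.

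**What to change.** Replace the closing sentence of SAP 7.5.2 with:

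*A completely missing stop date is treated as ongoing; the start-date conditions above (start before the last dose of the period, or before the last dose of bexagliflozin for the integrated summary) still apply.*

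This keeps the SAP's existing strict comparison with the last dose, so records with and without a stop date are tested in the same way. It also covers the integrated table. The section gives no rule for a missing or partial start date, and one could be added at the same time.

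The cost is one SAP sentence and one condition in the program that sets the period flags. No data collection, table layout or efficacy analysis changes.
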